## **2.0 OBJECTIVES**

This study will evaluate the local control rate of brachytherapy, cosmetic results, and complication rates when used as the sole method of radiation therapy for patients with

stage I and II ( $\leq 3$  cm) carcinoma of the breast treated with lumpectomy, with histologically negative surgical margins.

## **2.1 Primary Objective**

To determine if for DCIS and stage I and II breast cancer ( $\leq 3$  cm primary), brachytherapy will produce non-inferior local-regional control at 5 years compared to historical observed results with a conventional course of external beam radiotherapy (~94%)—(See 10.1.1)

## **2.2 Secondary Objectives**

- To determine if brachytherapy will have non-inferior toxicity to external beam radiotherapy (5%) at 3 years. Grade 3 or higher toxicity will be scored.
- To evaluate cosmesis at each follow-up by utilizing a cosmesis score based on established Harvard criteria.
- To assess patient satisfaction with breast brachytherapy by a questionnaire pre-brachytherapy, at completion, and post-brachytherapy.
- To perform a dosimetric comparison with an external beam plan for each patient. The following parameters will be evaluated: skin dose, target coverage, dose homogeneity index, and NTDmeans from dose volume histograms for each individual patient for heart, lung, and contralateral breast.
- To assess the ability to interpret mammography after interstitial brachytherapy.
- To evaluate Disease-free, Mastectomy-free, and Overall Survival.

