## **8.0 PATIENT ASSESSMENTS**

### **8.1 Study Parameters**

Assessment	Pre Rx	During/After Brachytherapy	Post RX 4-6 weeks	Post RX 6 mos.	Post RX 1 year
H & P (Initial Eval Form)	X				
Chest x-ray	X				
Lab studies a	X				
H & P (Follow-up Form)			X	X	Xc
Disease status	X		X	X	Xc
Toxicity Assessment		X	X	X	Xc
Mammograms	Xd			X	Xe
Cosmesis, Pt (Form)	X			X	Xb
Cosmesis, MD (Form)	X			X	Xb
Photographs	X	X	X	X	Xc
Questionnaire (QOL)	X	X	X	X	Xb

- a. CBC, platelets, PTT, PT, BUN, creatinine, lytes
- b. Yearly thereafter upto 5 years.
- c. Clinical examination and disease status assessment at 6 month intervals for the first 5 years and yearly intervals thereafter. (Can be done via clinic visit notes from other physicians involved in patient's care or via telephone follow-up).
- d. pre and post lumpectomy (if applicable)
- e. Every 6 months for 3 years and then yearly for 5 years (for treated breast) and yearly for opposite breast

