#### **At 4-6 wks, 6 mo., and 12 months after implant; q 6 months up to 5 years, then annually. Also at progression/relapse and at death**

- Follow-up Form (Appendix III) -- Can be done via clinic visit notes from other physicians involved in patient's care or via telephone follow-up

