## **10.0 STATISTICAL CONSIDERATIONS**

### **10.1 Study Endpoints**

#### **10.1.1 Ipsilateral breast recurrences**

This is a one-arm equivalence trial comparing the local failure rate in 300 patients receiving brachytherapy to the historical mean event rate of 6% (see Table below) among patients given external beam radiation. The null hypothesis thus is that brachytherapy is worse than external beam radiation; the alternative hypothesis is that the two regimens are clinically equivalent, meaning that brachytherapy is not significantly worse than external beam. Symbolically

$$H_0: \text{Pr}(\text{Local Failure, brachy.}) > \text{Pr}(\text{Local Failure, EB}) + \Delta$$

$$H_A: \text{Pr}(\text{Local Failure, brachy.}) \leq \text{Pr}(\text{Local Failure, EB}) + \Delta,$$

where "Pr()" denotes the probability of its argument and  $\Delta$  is the margin of clinical equivalence. That is, we consider two regimens whose event probabilities differ by less than  $\Delta$  to be equivalent. For this study we take  $\Delta$  to be 5%.

The analysis will be conducted by calculating an exact 95% confidence interval for the probability of local failure in the brachytherapy group and noting whether it includes 11% (obtained as  $\text{Pr}(\text{Local Failure, EB}) + \Delta = 6\% + 5\%$ ). If it does then we will not reject the null hypothesis and equivalence cannot be concluded. If the confidence interval for the probability of local failure given brachytherapy falls entirely below 11% then we conclude that brachytherapy is clinically equivalent (or possibly superior) to external beam radiation as a treatment for these patients. If, among 300 patients, there are 23 local failures (7.7%) then the exact 95% confidence interval for the true failure rate will be (5.2%, 11.2%). If there are 22 failures (7.3%) then the confidence interval will be (5.0%, 10.8%). Therefore we will reject the null hypothesis and conclude equivalence if we observe 22 or fewer local failures.

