### **10.1.2 Toxicity Assessment**

Patient will be seen on a daily basis by treating physician while receiving radiation therapy and during each follow-up visit. Toxicities resulting from brachytherapy will be collected and graded according to the Modified RTOG Toxicity Criteria (appendix). Any toxicities grade 3 or higher will be promptly reported to DSMB and IRB.

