### **10.2 Study Design**

The sample size will be approximately 300 patients. The toxicity rate will be summarized along with exact 95% confidence intervals. DFS, MFS and OS

results will be summarized using Kaplan-Meier curves with the usual Greenwood estimates of standard errors. Summary statistics will be given for cosmesis, quality of life, dosimetric, and mammography interpretation measures. All analyses will be conducted on an intent-to-treat basis; that is, all registered patients will be included in the analyses.

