## Appendix III: Follow-up Form

 If this is a revised or corrected form, indicate by checking box.		INSTRUCTIONS: Submit this form at the appropriate follow-up interval and whenever there is a change in the patient's status. Use -1 for unknown or not applicable unless otherwise specified in code table. Enter dates in mm-dd-yyyy.
PATIENT INITIALS: _____ STUDY ID #: _____ DATE OF EVALUATION ____-____-_____		CURRENT TUMOR STATUS
 # MONTHS SINCE BRACHYTHERAPY PROCEDURE		 NO EVIDENCE OF DISEASE
 PATIENT QUALITY OF LIFE FORMED COMPLETED?		 IPSILATERAL BREAST TUMOR RECURRENCE
 PATIENT COSMESIS FORM COMPLETED?		 LOCAL (infield) - within the prescription isodose volume
1 EXCELLENT 2 GOOD 3 FAIR 4 POOR		 PERIPHERAL - between the prescription isodose volume and a volume 2 cm outside of the prescription isodose volume.
 PHYSICIAN COSMESIS FORM COMPLETED? (Initials: _____)		 NON-CONTIGUOUS/EXTRA-FIELD - beyond the peripheral volume described above.
 RTOG TOXICITY SCORE: SKIN		 OTHER SITES OF CANCER RECURRENCE
GRADE 0 None GRADE 1 Slight atrophy; Pigmentation change; Some hair loss GRADE 2 Patch atrophy; Moderate telangiectasia; Total hair loss GRADE 3 Marked atrophy; Gross telangiectasia GRADE 4 Ulceration		 NODAL (Specify location) _____
 RTOG TOXICITY SCORE: SUBCUTANEOUS TISSUE		 CONTRALATERAL BREAST _____
GRADE 0 None GRADE 1 Slight induration (fibrosis) and loss of subcutaneous fat GRADE 2 Moderate fibrosis but asymptomatic; <10% linear reduction; Slight field contracture		 DISTANT METS (Specify location) _____
GRADE 3 Severe induration and loss of subcutaneous tissue; >10% linear measurement; Field contracture		 NEW PRIMARY LESION (Specify location) _____
GRADE 4 Necrosis		 MAMMOGRAM SINCE LAST VISIT
		1 No 2 Yes * *If yes, date of study _____-_____-
		 SUSPICIOUS FINDINGS ON MAMMOGRAM
		0 Not applicable/no mammogram 1 Negative mammogram 2 Microcalcifications only 3 Mass density only 4 Both, mass and microcalcifications 5 Other, Specify _____

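### Section 2.2 claims non-inferior toxicity to 5% at 3 years, but section 10.2 plans a crude rate without censoring and states no limit for it

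*Combined protocol and SAP*

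**What the plan says.** Section 2.2 (Secondary Objectives) makes an inferential claim: "To determine if brachytherapy will have non-inferior toxicity to external beam radiotherapy (5%) at 3 years". The event is any grade 3 or higher toxicity.

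Section 10.1.2 covers collection, grading and prompt reporting only. The analysis is one sentence in 10.2: "The toxicity rate will be summarized along with exact 95% confidence intervals". The analysis set follows in the same section: "All analyses will be conducted on an intent-to-treat basis; that is, all registered patients will be included in the analyses". Section 10.2 names Kaplan-Meier for disease-free, mastectomy-free and overall survival, but not for toxicity.

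The only margin is in 10.1.1, under the heading for ipsilateral breast recurrences. It is worded generally ("That is, we consider two regimens whose event probabilities differ by less than" delta count as equivalent) and delta is set at 5% for the study, but the two hypotheses are written for local failure.

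Toxicity is scheduled every 6 months to 5 years (8.1, footnote c), so a 3-year assessment is planned. The Follow-up Form in Appendix III provides for a grade that was not obtained: "Use -1 for unknown or not applicable unless otherwise specified in code table". No section says how such a patient enters the toxicity rate.

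**The concern.** There are two gaps between the objective and the analysis.

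- **Limit.** Non-inferiority needs an upper limit that the confidence interval must stay below. The primary endpoint has one (6% + 5% = 11%, at most 22 of 300, power 86%). For toxicity a reader has to infer it.
- **Loss before 3 years.** An exact binomial rate needs a known outcome for every patient in the denominator. With all registered patients in the denominator, someone last assessed event-free at 12 months contributes the same as someone examined and clear at 3 years. Late events after the last assessment are missed, and the error runs in the direction that favours brachytherapy.

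At stake is whether a statement that toxicity is no worse than external beam would be supported by the data. It is a secondary objective.

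**Working it through.** **Inputs from the documents.** n = 300; toxicity reference 5% at 3 years (2.2); exact 95% interval (10.2); delta = 5% (10.1.1); toxicity assessments every 6 months (8.1). **Assumed:** the 10% limit (5% + 5%), the proportion unassessed at 3 years, and the timing of loss.

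**1. The plan's own calculation.** For the primary rule, power = P(X ≤ 22) with X ~ Binomial(300, p). This gives 86.2% at 6%, 38.5% at 8% and 99.75% at 4%; section 10.1.1 states 86%, 39% and 99.8%. The method is reproduced. Clopper-Pearson upper limits are 10.9% for 22/300 and 11.3% for 23/300, slightly different from the printed 10.8% and 11.2%, but the cutoff of 22 stands.

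**2. The same method for toxicity.** Upper limit = the 97.5% point of Beta(x + 1, n − x).

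| Limit | Most events in 300 | Upper limit there | Upper limit, one more event | P(pass) at a true 5% |
|---|---|---|---|---|
| 10% (delta carried over) | 19 | 9.71% | 10.11% | 88.1% |
| 5% (no margin) | 7 | 4.75% | 5.19% | 1.6% |

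With complete assessment, the false-conclusion rate under the 10% limit is P(X ≤ 19) at a true 10% = 1.7%.

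**3. Effect of loss on the crude rate.** Assume a constant hazard with 10% cumulative incidence at 36 months, so F(t) = 1 − 0.9^(t/36). Let a fraction L be unassessed at 3 years, with last assessment equally likely at 0, 6, 12, 18, 24 or 30 months. The mean of F over those times is (0 + 0.0174 + 0.0345 + 0.0513 + 0.0678 + 0.0840)/6 = 0.0425. The probability that an event is recorded is q = (1 − L)(0.10) + L(0.0425). The false-conclusion rate is P(X ≤ 19) with X ~ Binomial(300, q).

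| L (assumed) | q | False non-inferior at a true 10% |
|---|---|---|
| 0 | 0.1000 | 1.7% |
| 5% | 0.0971 | 2.5% |
| 10% | 0.0943 | 3.6% |
| 20% | 0.0885 | 7.1% |

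A 95% interval aims at no more than 2.5% here, so the excess is negligible at 5% loss and material at 20%. A simulation with 20% loss gave 7.3% for even loss, 3.2% if losses fall only at months 30–36, and 14.4% if only at months 6–12.

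**4. A single data set.** Take 15 events and 60 event-free patients without a 3-year assessment (assumed). Keeping them gives 15/300 = 5.0%, interval 2.8% to 8.1%. Dropping them gives 15/240 = 6.25%, interval 3.5% to 10.1%. The first passes a 10% limit and the second does not. Dropping them discards event-free follow-up and overstates the rate, so a censored estimate lies between. Five events among the 60 would take 15 to 20, past the cutoff of 19.

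**5. The censored analysis.** The same simulation (150,000 runs per setting, constant hazard, non-informative loss, 5% competing events by 3 years, all assumed) applied the 10% limit to the cumulative-incidence interval. With 20% unassessed, the false-conclusion rate was 1.8–1.9% whatever the timing of loss.

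**The case against.** The strongest reply is that a limit exists. Section 10.1.1 sets delta for the study, not for one endpoint; 2.2 supplies the 5% reference; 10.2 uses the same exact interval as the primary. Together they give 10%, with power of 88%, close to the primary's 86%. This largely stands: 10% is the natural reading. What remains is that the hypotheses in 10.1.1 name only local failure, and nothing says that toxicity of twice the reference is acceptable.

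Second, 10.2 only summarises toxicity, so there is no written test whose error could be inflated, and no section says that unassessed patients count as event-free. That is also fair. The error rates above belong to the test that 2.2 implies, and the event-free count follows from putting every registered patient into a binomial denominator. They also depend on loss: at 5% unassessed there is little to correct.

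Third, a reader might infer that acute and late events are left wholly undefined. The documents do not support that. Section 9.1 lists a Treatment Toxicity Form at completion of brachytherapy, and the Follow-up Form carries the late skin and subcutaneous scales, so the forms already give a practical division.

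Fourth, a reader might see a contradiction between telephone follow-up ("Can be done via clinic visit notes from other physicians involved in patient's care or via telephone follow-up") and 10.1.2 ("Patient will be seen on a daily basis by treating physician while receiving radiation therapy and during each follow-up visit"). The two can coexist: one concerns visits that take place, the other contacts in place of a visit, and outside clinic notes can document an examination. It is at most a minor wording point to reconcile.

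**Conclusion.** The concern holds in two parts. The firmer one is the analysis method: a crude binomial rate over all registered patients cannot represent 3-year toxicity when some patients leave earlier, and it errs low. Under a 10% limit and even, non-informative loss, the false non-inferiority rate is about 2.5%, 3.6% and 7% for 5%, 10% and 20% unassessed, against 1.7% with none. The documents give no expected loss rate, so these are a range, not a prediction.

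The second part is a clarification: the limit is inferable as 10% but is not stated for toxicity. It would go too far to say that the plan has no usable limit or that any result could be called non-inferior.

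The local-failure conclusion does not depend on this point.

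**What to change.** 1. **Section 10.2.** For this objective, replace the crude rate with the cumulative incidence of first grade 3 or higher toxicity at 3 years and its 95% confidence interval, censored at the last toxicity assessment, with death as a competing event. This also settles that the 3-year figure is cumulative. Keep all grade 3 or higher events, as 2.2 states, and report acute (Treatment Toxicity Form) and late (Follow-up Form) events separately as well. Add a sensitivity analysis giving the number of events among unassessed patients that would change the conclusion.
2. **Section 2.2.** Either reword the objective as estimation, or state and justify a limit (for example, say explicitly whether the delta of 10.1.1 applies, giving 10%) and compare it with the upper 95% limit of the cumulative incidence.
3. **Minor.** Reconcile footnote c and 9.1 with 10.1.2 on telephone follow-up.

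**Cost.** Wording and a little analysis; assessment dates and deaths are already collected, and Kaplan-Meier is already planned for other endpoints. From the simulation with 20% unassessed, the interval at a true 5% widens from 5.1 to 5.4 points, and power under a 10% limit is about 83% (80–86% by timing of loss) instead of 88%. With 10% unassessed it is about 87%.

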## **3.0 PATIENT SELECTION CRITERIA**

### **3.1 Eligibility Criteria**

- Diagnosis of invasive ductal, medullary, papillary, colloid (*mucinous*), tubular histologies or Ductal carcinoma in situ (DCIS)
- Tumor stage: Tis, T1, T2 if lesion  $\leq 3$  cm
- Nodal Stage: N0 (*or a negative sentinel node mapping is acceptable*) or N1 (*1-3 nodes positive and no extracapsular extension*). This represents a cohort of patients that would not ordinarily receive axillary irradiation. (subjects with DCIS are exempt from nodal staging)
- Clearly visible target as defined by ultrasound, surgical clips, or mammography
- Unifocal breast cancer (*single focus which can be encompassed by one lumpectomy*)
- Negative microscopically-assessed surgical margins
- Negative post-lumpectomy mammogram if cancer presented with malignancy-associated microcalcifications
- No Paget's disease of the nipple or EIC by the Harvard definition, i.e. 1) more than 25% of the tumor is DCIS and there is DCIS in adjacent breast tissue, or 2) an intraductal carcinoma with microinvasion.
- No collagen vascular disease (systemic lupus erythematosis, scleroderma, or dermatomyositis)

- No previous radiation or chemotherapy for current breast cancer
- No co-existing medical conditions with life expectancy < 2 years
- Age > 18 years old
- No pregnant or lactating women.
- No psychiatric or addictive disorders which would preclude obtaining informed consent or completing the full series of brachytherapy treatments on an outpatient basis.
- Signed study-specific consent form

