**ELIGIBILITY CHECK****The following questions will be asked at registration:**

(Y) 1. Does the patient have histologically confirmed invasive ductal, medullary, papillary, colloid (*mucinous*), tubular cancer of the breast, or DCIS

(Y) 2. Is the AJCC T classification Tis, T1-2, N0-1, M0?

(Y) 3. Is the tumor size  $\leq$  3 cm.

(Y) 4. Are there  $\leq$  3 nodes positive without extracapsular extension?

(Y) 5. Does the patient have a well-defined target (ultrasound-defined seroma, surgical clips, or mammography)?

(N) 6. Has the patient undergone lumpectomy resulting in negative tumor margins? (*if yes, skip to Q8*)

(Y) 7. If no, is re-excision planned prior to introduction of radiation sources? (*failure to meet all criteria subsequent to re-excision will result in ineligibility*)

(Y/N) 8. Any evidence of pre-excision breast microcalcifications in the initial mammogram?  
 (Y) If yes, was a postoperative mammogram done and found negative for residual suspicious microcalcifications?

(N) 9. Any evidence of multicentric breast tumor, or unresolved suspicious synchronous tumors/calcifications

(N) 10. Any evidence of Paget's disease of the nipple, tumor involving skin, internal mammary or supraclavicular lymph nodes or distant metastasis?

(N) 11. Any evidence of collagen vascular disease or shortened life expectancy from coexisting medical conditions ( $< 2$  yrs)?

(N) 12. Any prior radiotherapy, chemotherapy or non-hormonal therapy for the present breast cancer?

(N) 13. Is the patient pregnant or lactating?

(Y) 14. Is the patient  $\geq$  18 years old?

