### **8.2 Response Criteria - Treatment failure**

- The definition of a treatment failure is: histologic evidence of recurrent carcinoma, either invasive or non-invasive (except LCIS) in the ipsilateral breast at 5 years.
- Ipsilateral breast recurrences will be considered **local (infield)** if they occur within the prescription isodose volume, **peripheral** if between the prescription isodose volume and a volume 2 cm outside of the prescription isodose volume. Ipsilateral recurrences will be considered **non-contiguous or extrafield** if they are beyond the peripheral volume described above.
- Ipsilateral axillary, infraclavicular, internal mammary, or supraclavicular recurrence or distant metastases will not be considered a treatment failure unless accompanied by ipsilateral breast recurrence.

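### The life-expectancy criterion (2 years) falls short of the 5-year primary endpoint, so patients who may die before year 5 are eligible and the crude count would treat them in effect as successes

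*Combined protocol and SAP*

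**What the plan says.** **Entry.** Section 3.1 lists "No co-existing medical conditions with life expectancy < 2 years". The schema carries the same criterion, and item 11 of the Eligibility Check asks about "shortened life expectancy from coexisting medical conditions", again with a limit of 2 years. There is no upper age limit.

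**Endpoint.** Section 2.1 asks whether "brachytherapy will produce non-inferior local-regional control at 5 years" against a historical figure of about 94%. Section 8.2 defines treatment failure as histologically proven recurrence "in the ipsilateral breast at 5 years". The toxicity objective in section 2.2 is read at 3 years.

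**Analysis.** Section 10.1.1 describes a one-arm trial "comparing the local failure rate in 300 patients receiving brachytherapy" with a historical 6%. An exact 95% interval for the failure probability must lie wholly below 11% (6% plus a margin of 5 points). The plan turns this into a rule: 22 or fewer failures among 300 means equivalence. Section 10.2 adds that "The sample size will be approximately 300 patients" and keeps every registered patient in the analysis. It names Kaplan-Meier for disease-free, mastectomy-free and overall survival, but not for local failure. Nothing states how a patient who dies or is lost before 5 years without recurrence is counted, and the sample size carries no stated allowance for such patients.

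**The concern.** The entry criterion and the endpoint use different time horizons, and the documents give no reason for the 2-year figure. A patient whose other illness leaves her 2 to 5 years meets every eligibility item, yet may well die before the time at which the primary question is answered. With the denominator fixed at 300, her death without recurrence adds one to the denominator and nothing to the numerator. In a trial that seeks to show the failure rate is not too high, that error favours the conclusion sought. If such patients were instead dropped or censored, the bias would be reduced, but fewer patients would carry 5-year information than the power statement assumes.

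**Working it through.** **1. The plan's own figures.** Let X be the number of failures among 300, binomial with probability p. Then P(X ≤ 22) is:

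- p = 6%: 86.2% (plan: 86%)
- p = 8%: 38.5% (plan: 39%)
- p = 4%: 99.75% (plan: 99.8%)
- p = 11%, the null boundary: 2.19%

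Clopper-Pearson limits are 4.7% to 10.9% for 22/300 and 4.9% to 11.3% for 23/300. They differ from the printed intervals by 0.1 to 0.3 points but give the same cut-off of 22. The 2.19% is the reference for what follows; the nominal ceiling for one side of a 95% interval is 2.5%.

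**2. Model for short-lived patients.** These are assumptions; the documents give no death rate. A share f of enrolled patients has an exponential death time with median 3 years. All patients have the same constant failure hazard, and failure and death are independent.

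- Failure hazard for a 5-year rate of 11%: h = −ln(1 − 0.11)/5 = 0.0233 per year
- Death hazard: μ = ln 2/3 = 0.2310 per year
- Observed 5-year failure in the short-lived group: g = h/(h + μ) × [1 − exp(−5(h + μ))] = 6.6%
- Crude rate in the trial: (1 − f) × 11% + f × g

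Since 6.6/11 is about 0.60, these patients still show some 60% of the failures they would have shown with full follow-up.

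**3. False equivalence, P(X ≤ 22) at the diluted rate**

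| Share f | Crude rate | False equivalence |
|---|---|---|
| 0 | 11.00% | 2.19% |
| 1% | 10.96% | 2.31% |
| 2% | 10.91% | 2.44% |
| 5% | 10.78% | 2.9% |
| 10% | 10.56% | 3.7% |
| 20% | 10.12% | 6.2% |

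In this group 1 − exp(−5μ) = 68.5% die within 5 years: about 10, 21 and 41 of 300 at shares of 5%, 10% and 20%.

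**4. A different assumption on timing.** Let d be the share of all patients who die failure-free before year 5. With d = 5%, 10% and 20%, false equivalence is 2.7%, 3.3% and 4.8% if deaths spread evenly over years 2 to 5, and 3.1%, 4.2% and 7.8% if they spread over years 0 to 5. In the extreme case where these patients show no failures at all, it is 4.2%, 7.8% and 21.6%.

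**5. If early deaths are removed from the denominator.** At f = 10% about 280 patients remain, the cut-off becomes 20, and power at 6% is 82.6%. This is not a clean measure of the loss, because exact power moves in steps with n: 84.2% at n = 276, 84.5% at n = 290, 82.6% at n = 295.

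**6. What a 5-year criterion would achieve.** It would still admit patients at the new limit. Setting the median to 5 years with f = 10% gives a crude rate of 10.70%, about 15 deaths (300 × 0.10 × 0.5) and false equivalence of 3.2%. The excess over 2.19% falls from about 1.5 to about 1.0 points, so roughly a third is recovered in that case.

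**The case against.** The strongest reply is that the entry criterion is not the main cause. The dilution arises because section 10.1.1 takes a crude count over 300 with no rule for early death. Deaths from breast cancer, unexpected deaths and losses to follow-up dilute in the same way whatever the entry limit. This stands, and it is why changing the criterion is only a partial remedy.

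A reader might infer that the flaw persists however early deaths are analysed. That holds only for lost precision: a time-to-event estimate that censors at death removes the bias if death is unrelated to recurrence risk, but it cannot recover follow-up that never happens.

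A reader might also infer that many such patients will enter, or that they contribute nothing. The documents support neither. The criterion permits them but gives no number; the background's mention of elderly women makes them plausible, no more. At a share of 1% or 2% the error stays below 2.5%. Section 8.1 schedules disease assessment every 6 months to year 5, so failures before death are observed.

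Two further points stand. Section 10.1.1 does not say whether the historical 5-year rates are crude or actuarial; if crude, the 6% benchmark shares some of the dilution. And a 2-year limit contradicts nothing else in the plan: wider access is part of the stated rationale, so a broad criterion can be defended if the sponsor gives the reason.

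**Conclusion.** The mismatch between a 2-year entry criterion and a 5-year endpoint is real, appears in all three places, and is not absorbed by the analysis or the sample size. Its direction is towards equivalence. Its size is unknown, because it depends on a share of patients that the documents do not give. With a median survival of 3 years, a constant failure hazard and independent death, the false-equivalence probability stays under 3% up to a share of 5% and reaches 3.7% at 10% and 6.2% at 20%. It is therefore a modest weakness, material only if the share is about 10% or more or if deaths come early. It does not show that the trial's conclusion would be wrong. Aligning the criterion is worth doing because it is cheap and removes a foreseeable source of partly informative patients, but it does not suffice alone.

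**What to change.** 1. In section 3.1, the schema and checklist item 11, align the life-expectancy criterion for co-existing conditions with the 5-year endpoint. This is a one-line amendment in three places. The cost is slightly slower accrual and a somewhat narrower population; fit elderly patients remain eligible. If the sponsor keeps 2 years, give the reason.

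2. In section 10.1.1, estimate 5-year local failure by cumulative incidence with death as a competing event, or by Kaplan-Meier, and compare the upper 95% confidence limit with 11%. State which, and why. Kaplan-Meier, censoring at death, removes the dilution if death and recurrence are independent. Cumulative incidence handles losses to follow-up and makes the role of death explicit, but with complete follow-up it equals the crude proportion, so the 11% limit must then be on the same basis. Say whether the historical rates are crude or actuarial.

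3. State how deaths and losses before 5 years are counted, and whether the sample size allows for them. As a guide, keeping 300 evaluable needs 300/0.95, or 316, registered if 5% are lost, and 300/0.90, or 334, if 10% are. The cost is a short revision of the statistical section and possibly some further accrual.
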